The HCW FGD will use the Consolidated Framework for Implementation Research (CFIR) to elicit information about health worker experiences with specific implementation strategies and opinions on modifications to these strategies to further improve implementation outcomes of fidelity and penetration.

PrEP Policy Maker and Implementer IDI: We will use qualitative methods to explore knowledge, attitudes, and beliefs about PrEP delivery strategies, preferred and essential attributes for PrEP delivery best practices, and experiences with PrEP delivery at national, county, or partner organization level.

12.2.6) LABORATORY METHODS

Not applicable

12.2.7) DATA COLLECTION INSTRUMENTS

- PrEP user focus group guide
- PrEP user demographic information
- HCW Survey
- HCW FGD guide
- Service Availability and Readiness Assessment Tool
- PrEP policy maker and implementer interview guide

12.2.8) VARIABLES: Outcomes, indicators, and source documents

Not applicable

12.2.9) TRAINING PROCEDURES

Drs. [name] and [name] will supervise training of facilitators for the qualitative components of the study.

Study Materials

- HCW FGD Consent Form
- HCW Survey Consent Form
- Policy Maker IDI Consent Form
- PrEP User FGD Consent Form

12.3 AIM 2:

To pilot and evaluate four strategies or bundles of strategies for optimized PrEP delivery for impact on penetration, fidelity, timeliness, efficiency, client and HCW satisfaction (including time), client PrEP knowledge, PrEP continuation, and PrEP adherence. We will test three strategies identified by stakeholders (based on qualitative information from Aim 1) and 1 pre-developed package of strategies (video counseling, HIVST, and optimized delivery). Operational definitions of each outcome are provided in Section *11.3.9 Variables*.

	Aim 2					
	Implementation strategy tests					
Population	HCW, clients attending study clinics					
Design	Interrupted time series (ITS) quasi-experimental design					
Data collection	Register abstraction of existing program data, client observation, quantitative surveys					
	Register abstraction of existing program data: unable to predict total number of records to be abstracted; expected abstraction of ~200 clients per month per clinic					
Sample size	Client observations: up to 200 clients per clinic per interrupted time series experiment cycle					
	Quantitative surveys: up to 240 clients per clinic per interrupted time series experiment cycle; up to 20 HCW per clinic per interrupted time series experiment cycle					
Outcome(s) of interest	PrEP penetration, fidelity, uptake, continuation, adherence, efficiency, timeliness, client and HCW satisfaction, client PrEP knowledge, service availability					
	HCW: work at a facility involved in study, involved in PrEP service delivery, >18 years					
criteria	Clients: female clients seeking health services at study facilities, >15 years (includes emancipated minors)					
Exclusion criteria	n N/A					

12.3.1) STUDY DESIGN

We will utilize interrupted-time series design; this is a quasi-experimental design that compares data before an intervention is introduced to data after the intervention is introduced, and controls for time trends (Figure 8). Four rounds of interrupted-time series evaluations to evaluate four PrEP optimization interventions, three identified by

stakeholders based on qualitative information in Aim 1, and one pre-developed package of interventions (video-based PrEP counselling, HIV Self-Testing [HIVST], and optimized PrEP delivery). Each of the four rounds of interrupted-time series evaluations will include 4 facilities receiving the intervention and 4 facilities serving as an ongoing concurrent comparator group; these 4 facilities will not receive any of the packages of interventions, but will undergo the same data collection procedures. There will be three months of baseline data collection and a three month intervention period for each of the 4 intervention facilities, and six months of data collection during the same calendar period for each of the 4 comparator clinics for each of the 4 interrupted-time series interventions.

Figure 8: Interrupted time series experiment design and timeline

12.3.2) INTERVENTION DETAILS

There will be four strategies or bundles of strategies tested, one bundle in each of the four interrupted-time series evaluations. Three of the bundles of strategies will be determined based on the qualitative information gathered

in Aim 1 by stakeholders and are unknown at this time. One bundle of strategies pre-developed is and includes 3 components: video-based PrEP counselling, HIV Self-Testing [HIVST] for women undergoing repeat HIV testing, and optimized PrEP delivery and prescription processes (Figure 9). We will work with a videography company to develop the PrEP video-based counseling component. We will borrow processes from ongoing and recently completed

Figure 9: Pre-determined bundle of implementation strategies

studies in western Kenya related for optimizing PrEP dispensing and HIVST while clients wait. PrEP will be stored in MCH clinics. Once women ask for PrEP and have been confirmed eligible, women will receive PrEP at MCH clinic. In our prior work, we have arranged with pharmacy and CCC to maintain supplies of PrEP at MCH. HIVST will be provided as an option in private cubicle-style kiosks, which have been tested in western Kenya and found to be acceptable and feasible.

12.3.3) STUDY POPULATIONS

The twenty (20) health care facilities that were included in Aim 1 surveys will be included in the implementation and evaluation of PrEP optimization strategies identified through Aim 1 activities. Of the 20 facilities, facilities will be assigned one of four intervention groups (4 facilities per group) or a comparator group (4 facilities) throughout the four interrupted-time series rounds. Up to twenty HCW will be approached at each facility per interrupted time series cycle to participate in a satisfaction survey to understand their experience with the PrEP optimization intervention.

During each of the four interrupted-time series rounds, we will abstract all clinical records for HIV-negative patients receiving MCH services to assess penetration of PrEP screening and PrEP uptake. We anticipate abstracting records for up to 200 clients per month per clinic (1,200 abstracted records per facility per interrupted-time series). Additionally, to assess intervention fidelity and client satisfaction through exit surveys with up to 40 clients per month per facility (240 exit surveys per facility per ITS). We will assess client time using client observation with up to 200 clients per clinic per interrupted-time series cycle.

12.3.4) SAMPLE SIZE DETERMINATION AND FORMULAS USED

To maintain the greatest amount of power, outcome estimates will be based on individual count data, not aggregated to summaries. We utilized Stata 14 for sample size calculations.

- Time period: Each experiment will include 3 months of data before each strategy is introduced and 3 months after each strategy is introduced
- Sample size (facilities): There will be 4 experiments, each will include 4 intervention facilities (16 facilities) and the same 4 comparator facilities; for a total of 20 facilities.
- Sample size (participants): We will observe 200 clients per clinic per experiment. We will collect survey data from 240 clients and 20 HCW per clinic per experiment. We will abstract register data during each experiment; while we are unable to predict total number of records to be abstracted, we expect abstraction of ~200 clients per month per clinic.
- Assumptions: α=0.05, two-sided tests, a conservative harmonic mean of 100 women presenting to ANC per month (~600 women over 6 months) per cluster (mean in PrIYA sites was ~163 per month), and a conservative estimate of the coefficient of variation of 0.5. We assume that penetration of PrEP screening and counselling is 68% (SD: 18%), time spent by HCW on PrEP services is 18 minutes (SD: 8 minutes) per PrEP initiator and 13 minutes (SD: 6 minutes) per PrEP-non-initiator, uptake is 10.5% (SD: 5%), and that knowledge and satisfaction scores are on a 100-point scale and have an SD of 20.

- Detectable effect size: We will be able to detect an absolute change of +/-4.8% for outcomes of penetration of PrEP screening, an absolute change of +/- 2 minutes in time, an absolute change of +/1% in PrEP uptake, and an absolute difference of 4 points in knowledge and satisfaction scores.
- Power: We will have at least 80% power

12.3.5) RECRUITMENT PROCEDURES

Register abstraction: We will not actively recruit individual participants for register abstraction.

Client observation: Women receiving MCH services will be approached as they enter the facility and asked to carry a time card. Each time card will collect the time that each service starts and ends and will be filled by providers, but will not collect any identifying information. Study staff will be posted at each facility until the sample size is reached.

Surveys with clients: Women receiving MCH services will be approached as they exit the facility and asked to participate in a brief survey. Study staff will be posted at each facility until the sample size is reached.

Surveys with HCW: HCW providing services will be approached by study staff in person, by phone or email and invited to complete a survey.

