Planned Analyses: We will use interrupted time series methodology to compare changes in penetration (PrEP screening), uptake (PrEP initiation), adherence, and continuation (PrEP refills) between the baseline and intervention periods for intervention facilities and with the comparison facilities.

12.3.7) LABORATORY METHODS

Not applicable

12.3.8) DATA COLLECTION INSTRUMENTS

- Exit Survey
- Record abstraction form

12.3.9) VARIABLES: Outcomes, indicators, and source documents

Outcome	Indicator	Source documents
PrEP penetration	Proportion of women who are screened for PrEP / total women receiving antenatal or postnatal services	Routine program data; PrEP register, antenatal register, postnatal register, family planning register
PrEP fidelity	Proportion of women who receive all PrEP specific steps in a visit: HIV testing, HIV risk screening, PrEP counseling	Primary data of anonymous exit survey assessing services received Direct observation of client-provider interactions
		Routine program data: HIV testing register, PrEP register, antenatal register, postnatal register, family planning register
PrEP uptake	Proportion of women who accept PrEP among those offered	Routine program data: PrEP register
PrEP continuation	Proportion of women who present for a refill among those initially prescribed PrEP	Routine program data: PrEP register, pharmacy records
PrEP adherence	Proportion of women who have >80% adherence to PrEP by pill count among those initially prescribed PrEP	Routine program data: PrEP register, pharmacy records
PrEP efficiency	Patient flow mapping to identify more efficient client flows with fewer transitions between physical spaces and providers	Primary data collection through direct observation of patient flow
Timeliness	Time and motion data to assess wait times, service delivery times, and HCW burden	Primary data collection through direct observation and time collection
Client satisfaction	Satisfaction on a scale of 1-10 adapted from Training Satisfaction Survey	Primary data collection through anonymous surveys
HCW satisfaction	Satisfaction on a scale of 1-10 adapted from Training Satisfaction Survey	Primary data collection through anonymous surveys
Client PrEP knowledge	10 questions based on content covered in counseling sessions	Primary data collection through anonymous surveys

12.3.10) TRAINING PROCEDURES

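### Section 12.3.4 claims 80% power for a 4-point difference in satisfaction scores without separating clients from health care workers (HCW), and 20 HCW per clinic cannot deliver it

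*Combined protocol and SAP*

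**What the plan says.** The power statement is in section 12.3.4. Its assumptions are "α=0.05, two-sided tests" and that "knowledge and satisfaction scores are on a 100-point scale and have an SD of 20". The detectable effect it gives is "an absolute difference of 4 points in knowledge and satisfaction scores", and it adds: "We will have at least 80% power". One SD and one detectable difference serve all knowledge and satisfaction scores.

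The survey numbers are in the same section: "We will collect survey data from 240 clients and 20 HCW per clinic per experiment". Section 12.3.3 makes the HCW number a ceiling on those invited: "Up to twenty HCW will be approached at each facility per interrupted time series cycle". Each experiment has four intervention and four comparator facilities, with three months of baseline and three months of intervention (section 12.3.1).

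The Aim 2 summary table lists client and HCW satisfaction among the outcomes. Section 12.3.9 gives each its own row, both reading "Satisfaction on a scale of 1-10 adapted from" a named survey. Client knowledge is measured by "10 questions based on content covered in counseling sessions". No scoring or conversion rule is given for any of the three.

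**The concern.** Clients outnumber HCW by 12 to 1 in the survey plan (240 against 20 per clinic), so one detectable difference at one SD cannot hold for both. If 4 points is right for clients, it must be too small for HCW.

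At stake is how an HCW satisfaction result would be read. Section 12.3.4 offers the only sensitivity figure for this outcome. A comparison showing no difference would be set against a stated 4 points when the design could reliably detect only something more than twice as large. The Aim 3 stakeholder workshop will review the Aim 2 findings and draft best practices, so the stated precision has readers outside the study team.

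Separately, the power statement is on a 100-point scale while the outcome table describes a 1-10 rating and ten questions. The link between them is not written down.

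**Working it through.** **Inputs.** From section 12.3.4: two-sided alpha 0.05, power 80%, SD 20, difference 4, and 240 clients and 20 HCW per clinic per experiment. From section 12.3.1: four clinics per arm and two three-month periods. From section 12.3.3: up to 40 client surveys per month per facility. The protocol names Stata 14 but gives no formula, so I used the normal approximation for two means with individuals treated as independent.

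- Required size: n per group = 2 × SD² × (1.960 + 0.842)² / d²
- Detectable difference, two groups: (1.960 + 0.842) × SD × √(2/n)
- Detectable difference, difference-in-differences: (1.960 + 0.842) × SD × √(4/n), with n per cell
- Power for 4 points: Φ(4/SE − 1.960), where SE = SD × √(2/n), or SD × √(4/n) for difference-in-differences

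**Step 1: the plan's figure.** For d = 4 and SD 20, n = 2 × 400 × 7.849 / 16 = 392.4, so 393 per group.

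**Step 2: clients.** 40 per month × 3 months × 4 clinics = 480 per group, either before against after in the intervention clinics or intervention against comparator in one period. The detectable difference is 2.802 × 20 × √(2/480) = 3.6 points, with 87% power for 4. The stated claim is reproduced for clients on this simple comparison, ignoring clustering.

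**Step 3: HCW, same formulae, clustering ignored.**

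| Comparison | Size | Detectable difference | Power for 4 points |
|---|---|---|---|
| All 20 per clinic, intervention vs comparator | 80 vs 80 | 8.9 | 24% |
| 20 per clinic split before/after | 40 vs 40 | 12.5 | 14% |
| Difference-in-differences | 40 per cell | 17.7 | 9% |
| All four experiments pooled | 320 vs 320 | 4.4 | 72% |

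For example, 2.802 × 20 × √(2/80) = 8.86. The pooled row is generous: its comparator side is 4 clinics × 20 × 4 rounds, so the same four clinics are counted four times. Detecting 4 points within one experiment would need 393/4, about 98 HCW per clinic, against 20 planned. Alternatively, with 80 per group the SD would have to be about 9.0 or less: 4 / (2.802 × √(2/80)) = 9.03.

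**Step 4: clustering.** The documents give no intraclass correlation. Assuming 0.01 to 0.05 and 20 HCW per clinic, the design effect 1 + 19 × ICC is 1.19 to 1.95, and the 80 vs 80 figure rises from 8.9 to between 9.7 and 12.4. HCW surveys are anonymous (section 12.3.6), so pairing individuals before and after is not available to recover precision.

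**Step 5: the scale.** Any linear conversion to 100 points multiplies the difference and the SD by the same factor. The ratio 4/20 = 0.2 is unchanged, and so is the power. The scale mismatch therefore has no effect on steps 1 to 4.

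**The case against.** **Section 12.3.4 may have meant client satisfaction only.** That is possible, and the match with client numbers in step 2 supports it. But the text does not say so, and the same section lists the 20 HCW per clinic as part of the survey sample. If clients only were meant, HCW satisfaction has no stated sensitivity and the same sentence still needs limiting.

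**No HCW comparison is specified.** The planned interrupted time series analyses in section 12.3.6 name penetration, uptake, adherence and continuation, not satisfaction. The HCW survey asks about the training and the changes to service delivery, which has no obvious baseline or comparator counterpart. This stands: the contrasts in step 3 are candidates, and the documents do not settle which applies. On the other side, HCW satisfaction is a listed outcome and comparator facilities undergo the same data collection. No candidate reaches 80% power for 4 points, pooling included. If no comparison is intended, the outcome is descriptive and should be called so.

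**The scale mismatch does not touch power.** This stands in full. A reader might infer that 4 points on a 1-10 rating is an absurdly large threshold, or that an SD of 20 is impossible there. The documents do not support that reading. Section 12.3.4 ties both figures to its own 100-point scale, it states a detectable difference and not a decision threshold, and ten questions scored as percent correct would already be on 100 points. What is missing is a scoring rule.

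**Conclusion.** The 4-point statement is wrong as written, because it covers HCW satisfaction without exception. At SD 20 and up to 20 HCW per clinic, the detectable difference within one experiment is no better than about 8.9 points of 100, 2.2 times the stated 4 (8.9/4). It is about 12.5 with a before/after split and 17.7 with a difference-in-differences. These figures assume that the SD of 20 applies to HCW, that all 20 respond at every clinic, and that clustering is nil. Non-response or clustering would make them worse; a smaller SD would make them better.

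For clients the figure is consistent with a two-group comparison that ignores clustering. That is a check of the plan's arithmetic, not an endorsement for every analysis: a client difference-in-differences with 480 per cell detects 5.1 points and has 59% power for 4.

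A reader might also want replacement figures in instrument units. The documents give no SD for the 1-10 rating or the ten-question score, and rescaling the assumed 20 would add no information. The scale question is a minor clarification.

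**What to change.** In section 12.3.4, limit the 4-point statement to client knowledge and client satisfaction. For HCW satisfaction, do one of two things:

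- label it descriptive; or
- name the comparison and state a separate detectable difference, no better than about 9 points of 100 at SD 20 and larger once clustering or a before/after contrast is allowed for.

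As a minor clarification, state in section 12.3.9 how the 1-10 satisfaction rating and the ten knowledge questions are converted to the 100-point scale used in section 12.3.4.

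The descriptive option is a change of wording only. The second option also needs a named analysis and an assumed intraclass correlation, and leaves a less favourable stated figure for HCW satisfaction. Neither requires more respondents or a change of design.

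### Section 12.3.4 claims 80% power for a 4.8-point change in penetration without naming the contrast, and its stated inputs do not deliver that for the planned trend-controlled analysis with comparators

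*Combined protocol and SAP*

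**What the plan says.** - **Power statement (12.3.4).** "We will be able to detect an absolute change of +/-4.8% for outcomes of penetration of PrEP screening", followed by "We will have at least 80% power". The level is two-sided 0.05. No formula is shown; only the software is named.
- **Volume (12.3.4).** The assumption is "a conservative harmonic mean of 100 women presenting to ANC per month", about 600 women per clinic over six months, against a mean of about 163 per month in an earlier programme. For register data, "we expect abstraction of ~200 clients per month per clinic".
- **Variation (12.3.4).** Penetration is taken as 68% with SD 18%, alongside "a conservative estimate of the coefficient of variation of 0.5". The level to which either figure applies is not given.
- **Unit (12.3.4).** "outcome estimates will be based on individual count data, not aggregated to summaries".
- **Design (12.3.1).** The interrupted time series "compares data before an intervention is introduced to data after the intervention is introduced, and controls for time trends". Each round has 4 intervention facilities and 4 concurrent comparators, with 3 baseline and 3 intervention months.
- **Analysis (12.3.6, Planned Analyses).** Baseline and intervention periods are compared within intervention facilities, and also with the comparison facilities. No model is written down there or in Section 15.
- **Denominator (12.3.9).** Penetration counts women in antenatal or postnatal care, not ANC alone.
- **Alternatives (Section 16).** Classical pre-post and difference-in-differences designs were considered and set aside as weaker on temporal trends and on heterogeneity between clinics.

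**The concern.** A power figure belongs to a particular contrast. Measuring the change against comparators adds the comparators' own before-and-after sampling error, and fitting trends over only 3 + 3 months adds more. The unqualified 80% is therefore unlikely to hold both for a plain before-after change and for the trend-controlled comparison that 12.3.1 and 12.3.6 describe.

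What is at stake is how a null result is read. If the comparison with comparators has 42-50% power at the assumed volume, it misses a true 4.8-point change 50-58% of the time. A reader told that power was 80% could give such a null more weight than it can bear.

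**Working it through.** **Inputs.** From 12.3.4: two-sided 0.05, 80% power, 68% penetration, SD 18%, 100 women per clinic-month, 4 + 4 clinics, 3 + 3 months. Women per group-period: n = 4 × 3 × 100 = 1,200 (1,956 at 163 per month; 2,400 at 200). z = 1.960 + 0.842 = 2.802. Power = Φ(0.048/SE − 1.960). Clinic-by-period variation is set to zero, which is favourable to the plan.

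**Variances.** 68%: 0.68 × 0.32 = 0.2176. After a rise to 72.8%: 0.1980. After a fall to 63.2%: 0.2326. If SD 18% is between-clinic and the analysis is stratified by clinic, subtract 0.18² = 0.0324 from each: 0.1852, 0.1656 and 0.2002.

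**Step 1: what gives 4.8 points.** Before-after in the 4 intervention clinics, SE = √((v1 + v2)/n):
- Unstratified: rise √(0.4156/1200) = 0.0186, power 73%; fall √(0.4502/1200) = 0.0194, power 70%.
- Stratified rise: √(0.3508/1200) = 0.0171, power 80.2%, detectable 2.802 × 0.0171 = 4.79 points.
- Stratified fall: √(0.3854/1200) = 0.0179, power 76.4%, detectable 5.02 points.

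So the stated figure is matched by an uncontrolled before-after rise, stratified by clinic. Even then it does not hold in both directions.

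**Step 2: change against comparators with shared period effects.** Three cells stay at 68% and one moves, so SE = √((3·v1 + v2)/n):
- Unstratified: rise √(0.8508/1200) = 0.0266, power 43.8%; fall √(0.8854/1200) = 0.0272, power 42.4%. A simulation of this case gave 43.8% and 42.2%.
- Stratified: rise √(0.7212/1200) = 0.0245, power 49.9%; fall √(0.7558/1200) = 0.0251, power 48.1%.

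Detectable change with baseline variance in all four cells: 2.802 × √(4 × 0.2176/1200) = 7.5 points, or 7.0 stratified. At n = 2,400: 5.3 and 4.9. Reaching 80% for 4.8 points needs 205-251 women per clinic-month.

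**Step 3: other trend structures.** Variance factors relative to before-after, from design matrices with 3 + 3 monthly points, multiply the Step 1 variances. Ranges run from an unstratified fall to a stratified rise.

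| Model | Factor | Power, 100/month | Power, 200/month |
|---|---|---|---|
| Before-after, intervention clinics only | 1 | 70-80% | 94-98% |
| Comparators, shared linear trend only | 1.63 | about 49-59% | about 78-88% |
| Comparators, shared period effects (same factor if a shared trend is added) | 2.0 | 42-50% | 71-79% |
| Single group, linear trend | 4.375 | 22-27% | 39-48% |
| Comparators, group-specific trends | 8.75 | 13-16% | 22-26% |

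At 163 per month the shared-period contrast has 62-71%.

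**Step 4: the CV.** 18/68 = 0.26, whereas a CV of 0.5 implies an SD of 0.5 × 68 = 34 points. If 34 points were the between-clinic SD and stratification removed it (0.2176 − 0.1156 = 0.1020 at baseline), power at 100 per month would be 73-76% with shared period effects and about 80-86% with a shared linear trend.

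**Step 5: clinic-by-period variation.** The documents give no figure, so this is an assumption. An SD of 1, 2 or 3 points adds 2·s²/4 to the before-after variance and lowers the stratified before-after power at 100 per month to 70-74%, 56-58% or 41-42%.

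**The case against.** The strongest reply is that no arithmetic error has been shown. The planned analyses include a comparison of periods within intervention facilities, 4.8 points can be reproduced for that, and 12.3.4 never ties the figure to the comparators. This stands in part: what can be shown is an unnamed contrast and a claim too broad for the planned analysis, not a miscalculation.

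A second reply is that the model is open. Depending on trend terms and on the reading of CV 0.5, comparator power at 100 per month runs from about 13% to over 80%. The same 4 comparators also serve all four rounds, which the timeline places consecutively. If one linear trend were assumed to hold over those 24 months and to be shared by the intervention clinics, the variance factor would be about 1.01 and power 69-80%. That is a strong assumption which the plan does not make, but it shows that 42-50% is not inherent to using comparators.

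A third is that 100 is called conservative and covers ANC women only, whereas the penetration denominator is wider. This is fair, although 12.3.3 gives 200 as an upper expectation. At 200 the shared-linear-trend model is about at 80%; the shared-period contrast still falls short.

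Three stronger readings are tempting and not supported:
- That 42-50% is the power of the experiment. It belongs to one model, and the documents specify none.
- That the authors used a before-after formula, so that 4.8 points applies only there. This is an inference from a match. The same recipe for uptake (10.5%, SD 5%) gives 2.802 × √(2 × (0.0940 − 0.0025)/1200) = about 3.5 points, not the stated 1.
- That policymakers will be shown a false null. Section 12.4.5 uses penetration inside a hypothetical vignette, and nothing says that a null test will be presented as no effect.

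**Conclusion.** The concern holds in this form: the unqualified 80% for ±4.8 points is not supported, on the stated inputs, for the trend-controlled analysis with comparators. At 100 women per clinic-month and SD 18%, every comparator or trend model in the table falls below 60%, and the shared-period contrast has 42-50%. The one calculation that reaches 80% is an uncontrolled before-after rise with clinic variance removed; a fall has 76%.

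A larger volume narrows the gap, and reading CV 0.5 as between-clinic spread would narrow or close it. The first departs from the volume that 12.3.4 lists among its power assumptions. The second conflicts with its SD of 18%. All these figures assume no clinic-by-period variation, and any such variation lowers them.

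Confidence is high that the 80% statement is unsupported for the planned analysis, and moderate for any single replacement figure, because the model is not specified.

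**What to change.** In 12.3.4, state:
- the contrast to which the power refers (within intervention facilities, or change against comparators) and the trend terms fitted;
- the monthly volume used, and whether it counts ANC women only or all antenatal and postnatal women;
- what SD 18% and CV 0.5 each describe and how they enter the calculation.

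Then replace ±4.8 points at 80% with the detectable change, or the power, recomputed for the planned analysis. As an illustration only, change against comparators with shared period effects detects about ±7.0 to 7.5 points at 100 per month and ±4.9 to 5.3 at 200, before any clinic-by-period variation. Group-specific trends would make these larger.

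The cost is a recalculation and a few sentences. No participants, facilities or data collection change. The only downside is a less favourable stated figure.

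### The design does not deliver the stated 80% power for a 1-point change in uptake, nor for a 4.8-point change in penetration measured against the comparator facilities

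*Combined protocol and SAP*

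**What the plan says.** Section 12.3.1 describes four interrupted time series experiments, each with three months before and three months after a strategy is introduced, in "4 facilities receiving the intervention and 4 facilities serving as an ongoing concurrent comparator group". It presents the design as one that adjusts for trends over time. Under Planned Analyses, section 12.3.6 compares baseline with intervention periods in the intervention facilities, and also with the comparison facilities. It names no model and no variance term, and section 15 adds none.

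Section 12.3.4 gives the power statement. Its inputs are a two-sided 5% level, a harmonic mean of 100 women per facility per month (the earlier PrIYA sites averaged about 163, and about 200 records per month are expected), "a conservative estimate of the coefficient of variation of 0.5", and penetration of 68% with SD 18%. For uptake the input is "uptake is 10.5% (SD: 5" per cent. Knowledge and satisfaction scores have SD 20 on a 100-point scale. The outputs are:

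- penetration: "We will be able to detect an absolute change of +/-4.8% for outcomes of penetration of PrEP screening"
- uptake: "an absolute change of +/1% in PrEP uptake"
- scores: "an absolute difference of 4 points in knowledge and satisfaction scores"
- power: "We will have at least 80% power"

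On the unit of analysis the section says: "To maintain the greatest amount of power, outcome estimates will be based on individual count data, not aggregated to summaries". Section 12.3.9 defines uptake among women offered PrEP.

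**The concern.** A 1-point change from 10.5% is very small for a yes/no outcome observed in one to two thousand women per group. The stated SDs of 18% and 5% cannot be woman-level SDs of proportions at 68% and 10.5%. The section also does not say whether its figures refer to the change within intervention facilities or to that change relative to comparators. The second is the contrast that uses the concurrent comparator group, and its variance is twice as large.

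At stake is how Aim 2 will be read. A null result could be taken to exclude changes of about 5 points in penetration or 1 point in uptake, which these data cannot do. Under section 12.4.5, Aim 2 data go into the reports for the best-practices workshop, and penetration is the only effectiveness information first shown to policymakers in the budget impact interviews.

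**Working it through.** **Inputs.** From section 12.3.4: two-sided 5%, 80% power, n = 100, 163 or 200 women per facility per month, penetration 68%, uptake 10.5%, score SD 20, 240 surveys per facility per experiment. From section 12.3.1: 4 versus 4 facilities and 3 + 3 months. The normal multiplier is 1.960 + 0.842 = 2.802. Facility-by-period SDs are not in the documents, so any value used for them is an assumption.

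**1. Trying to reproduce the stated figures.** With the stated SDs treated as woman-level SDs, the two-group size is 2 × (2.802 × SD / effect)²:

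- penetration (18, 4.8): 221 per group
- time, initiators (8, 2): 251
- uptake (5, 1): 392
- scores (20, 4): 392

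No single group size gives all four. Uptake is recovered at 400 per group (2.802 × 5 × √(2/400) = 0.99), but penetration at 400 is then 3.6, not 4.8.

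**2. Woman-level variance.** Penetration: V = 0.68 × 0.32 = 0.2176 (SD 46.6 points). Uptake: V = 0.105 × 0.895 = 0.0940 (SD 30.7 points).

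**3. Two contrasts, with independent women, no drift and no trend term.** Each facility group contributes 12n women per period (4 facilities × 3 months).

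- Change against comparators (four cells): SE = √(4V/12n) = √(V/3n)
- Pre-post in intervention facilities only (two cells): SE = √(2V/12n)

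For penetration against comparators at n = 100, SE = √(0.2176/300) = 0.0269, and 2.802 × 0.0269 = 7.5 points.

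| Outcome (stated effect) | n/month | Against comparators: detectable (power) | Pre-post: detectable (power) |
|---|---|---|---|
| Penetration (4.8) | 100 | 7.5 (43%) | 5.3 (71%) |
| | 163 | 5.9 (62%) | 4.2 (90%) |
| | 200 | 5.3 (71%) | 3.8 (95%) |
| Uptake (1) | 100 | 5.0 (9%) | 3.5 (13%) |
| | 200 | 3.5 (13%) | 2.5 (20%) |

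For 4.8 points at 80% power, n = V × (2.802/0.048)² / 3, about 247 per month, against comparators, and half that, about 124, pre-post. For 1 point in uptake, a two-group contrast needs 2 × (2.802 × 0.3066/0.01)², about 14,750 women per group. Four facilities over three months supply 1,200 (n = 100) to 2,400 (n = 200).

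**4. Uptake among women offered PrEP.** If 68% are offered it (an assumption), 204 or 408 women remain per facility-period. The detectable change against comparators is then 6.0 or 4.3 points, with power for 1 point of 8% or 10%.

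**5. Scores.** With 120 surveys per facility-period, SE = 20 × √(1/120) = 1.83. The detectable difference against comparators is 5.1 points, and power for 4 points is 59%. A pre-post contrast of 480 versus 480 gives 3.6.

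**6. Facility-by-period variation (SD s, assumed).** Against comparators, SE = √(s² + V/3n). At s = 2 points, power for 4.8 points is 30% (n = 100) to 41% (n = 200). At s = 5 it is 13% to 15%. Once s exceeds 4.8/2.802 = 1.7 points, no number of records reaches 80%. For uptake that limit is 1/2.802 = 0.36 points.

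**7. Arm-specific trends.** With a linear trend and a level change in each arm over 3 + 3 months, SE = √(s² + 1.458V/n). At n = 100 and s = 0 this is 0.0563, or 15.8 points detectable. At n = 200 it is 11.2 points.

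**8. Illustration of false-positive risk, under assumed SDs.** If the model in step 7 were fitted with binomial variance only, the error rate would be 2Φ(−1.96 × nominal SE / true SE). At n = 100 and s = 5, the nominal SE is 0.0563 and the true SE is √(0.0025 + 0.00317) = 0.0753, so the rate is 14%. At s = 2 and 3 it is 6–7% and 8–9%. The plan does not say that it will analyse the data this way.

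**The case against.** The strongest defence concerns penetration. Section 12.3.6 names a within-facility comparison as well as one with comparators, and section 12.3.4 speaks only of an absolute change. On the within-facility contrast, power for 4.8 points is 90% at 163 women per month and 95% at 200. If the coefficient of variation of 0.5 refers to cluster size (an assumption), a harmonic mean of 100 implies an arithmetic mean of about 100 × (1 + 0.5²) = 125, and the pre-post detectable change is then 4.8, the stated figure. This stands as far as it goes, so a reader should not infer that 4.8 fails on every contrast. It does not support the claim for the comparator-controlled contrast, and section 16 says that a classical pre-post design was considered and not chosen. At 125 per month, uptake still gives 3.1 points pre-post and 4.4 against comparators.

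Three other stronger readings are tempting, and the documents do not support them:

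- **Clustering was left out of the calculation.** A coefficient of variation is stated. Its role is undefined and no ICC is given, so the documents do not show what was done.
- **The argument for individual-level data is false.** It is conditional. With unequal facilities and little drift, weighting by individuals can be more precise than unweighted facility summaries. Individual-level data do not, however, remove facility-by-period variation.
- **The analysis will inflate the false-positive rate.** Section 12.3.6 is silent on variance terms, and silence is not omission. Section 15 also has the data monitoring committee review a statistical analysis plan, which may name a model.

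The 15.8 points in step 7 hold the variance at its 68% value. For an increase of that size the post-period variance falls and the figure is about 15. Aim 2 is also partly a pilot with a fixed set of facilities. That favours reporting estimates, but does not support the stated power.

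**Conclusion.** The power statement is wrong as written. For uptake it fails on both contrasts once uptake is treated as a proportion: power for 1 point is 9% to 20% with every woman as denominator, and lower among women offered PrEP. For penetration it fails on the comparator-controlled contrast at every volume in the plan (43% to 71%), and holds only for an uncontrolled pre-post change at about 125 women per month or more. The 4-point score figure also fails against comparators.

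These results assume independent women and no facility drift, which favours the plan, and they need no assumed ICC. Only the sizes of the further losses in step 6 and the error rates in step 8 rest on assumed SDs. I make no claim about the time outcome.

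**What to change.** In section 12.3.4:

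- State that the power statement refers to the change in intervention facilities relative to comparators.
- Define the coefficient of variation of 0.5, and give the ICC or variance components used.
- Restate the detectable effects for that contrast: binomial variance for penetration and uptake, women offered PrEP as the uptake denominator, and a range of facility-by-period SDs. Restate the scores on the same contrast. If trends are arm-specific, the figures should be those for the trend model.
- If the individual-level rationale is kept, add that such data do not remove facility-by-period variation.

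In section 12.3.6, name an analysis whose standard errors allow for facility-by-period variation. Examples are a random facility-by-period effect with small-sample degrees of freedom, or a facility-level comparison of 4 versus 4. The choice is the sponsor's. Label any error-rate figures as illustrations under assumed SDs.

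If the restated effects are not plausible, drop the 80% power claim and present Aim 2 as estimation with confidence intervals.

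The cost is revised wording, a recalculation and modest analysis work, with no new data. The downside is less favourable stated effects and wider intervals. For example, a facility-level t-test on 6 df without a trend term (multiplier 3.367) detects 9.1, 7.1 and 6.4 points in penetration at 100, 163 and 200 women per month, even with no drift.
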